5 STUDY DESIGN

The study will be prospective, multi-center, unblinded, randomized, controlled, non-inferiority study, comparing the HM3 LVAS to the HM II LVAS. Short term use of the device will be evaluated when Subjects have been supported for 6 months. Long term use of the device will be evaluated when Subjects have been followed for 24 months.

Subjects who receive a device exchange to any device other than HM II or HM3, at any time during the study, will be withdrawn from the study and will not be followed.

[figure not shown]
This study will be conducted as a staged pivotal study that includes a pre-specified early assessment for safety that is consistent with FDA's new Guidance for staged approval process, and in accordance with applicable local and federal regulations as specified in 21 CFR part 812.

During the early safety phase of the pivotal study, up to 5 centers in the United States (U.S.) will be initiated to enroll up to 10 randomized HM3 Subjects. A pre-specified analysis for safety will be performed after the first 10 randomized HM3 Subjects have completed 30 day follow-up. The results of this early safety analysis will be reviewed by the Data Safety Monitoring Board (DSMB), after which the DSMB report, along with supporting safety data from the HM3 CE Mark study will be sent to FDA as an IDE supplement, with a request to gain full IDE approval to expand the study to up to a total of 60 centers in the U.S. The first 5 U.S. centers will continue to enroll up to a total of 30 subjects (including those in the early safety analysis) during FDA's review of this IDE Supplement.

The study will include an adaptive design which will be used, if required to adjust the sample size at a pre-specified time during the study.

In addition to the primary study endpoint, the study will include a powered secondary endpoint to provide supplemental data for HM3 labeling.

Figure 2 – MOMENTUM 3 IDE Study Flow

Total sample size = 1028 (randomized 1:1).

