13.9 Analysis of Survival and Subject Outcome

Overall survival will be assessed for each of the two treatments using the Kaplan-Meier product-limit method. Differences between treatments in survival distributions will be analyzed using a logrank test. Subjects surviving will be censored at last known follow-up time point.

A competing outcome graph will be prepared at 6 months for short term results and 24 months for long term results.

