22 SUBJECT WITHDRAWAL

The Subject retains the right to withdraw from the study at any time. Should the Subject elect to withdraw from the study, the reason for withdrawal must be documented in the CRF.

Reasons for withdrawal include:

- Subject chooses to withdraw
- Investigator decides to withdraw Subject
- Subject has pump exchanged to any device other than HM II or HM3
- Subject is not implanted with device after randomization.
 - Any subject that is not immediately implanted after randomization, due to deterioration or improvement of their health status, will be followed to implant or outcome or until the cohort is fully enrolled at which time they will be withdrawn as follows:
 - For the short term and long term cohorts, any subject not implanted or who has not achieved an outcome 30 days after the 366th subject is enrolled will be withdrawn.
 - For the powered secondary endpoint, any subject not implanted or who has not achieved an outcome 30 days after the 1028th subject is enrolled will be withdrawn.

- Subject is lost to follow-up
 - Subjects who can no longer be tracked for follow-up data collection at a participating MOMENTUM 3 center will be formally withdrawn from the study.

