8.2 Study Hypothesis

8.2.1 Short Term Support:

The short term study endpoint is a composite of survival to transplant, myocardial recovery or 6 months of support (whichever occurs first) free of a debilitating

stroke (modified Rankin Score > 3) or reoperation to replace the original pump. A Subject will be considered a success if they are:

- Electively transplanted or explanted for myocardial recovery prior to 6 months or
- Alive at 6 months, and
 - Have not experienced a stroke with a modified Rankin Score > 3, and
 - Have not received a device replacement or exchange, and
 - Have not received an urgent transplant due to a LVAS malfunction.

A Subject will be considered a failure if they:

- Expire prior to 6 months, or
- Experience a stroke with a modified Rankin Score > 3 prior to 6 months, or
- Have a device replaced or exchanged or deactivated for reasons other than myocardial recovery prior to 6 months, or
- Have received an urgent transplant due to a LVAS malfunction prior to 6 months, or
- Have withdrawn from the study for any reason prior to 6 months

HM III short term success rate will be compared to that of the HM II control in a non-inferiority manner. The null and alternative hypotheses are:

$$H_0: \pi_{HM III} \leq \pi_{HM II} - \Delta$$

$$H_A: \pi_{HM III} > \pi_{HM II} - \Delta$$

where $\pi_{HM III}$ and $\pi_{HM II}$ are the short term success rates of HM III and HM II, respectively, and where Δ is the non-inferiority margin.

8.2.2 Long Term Support:

The long term study endpoint is a composite of survival to transplant, myocardial recovery or 24 months of support (whichever occurs first) free of a debilitating stroke (modified Rankin Score > 3) or reoperation to replace the original pump.

A Subject will be considered a success if they are:

- Electively transplanted or explanted for myocardial recovery prior to 24 months or
- Alive at 24 months, and
 - Have not experienced a stroke with a modified Rankin Score > 3, and
 - Have not received a device replacement or exchange, and
 - Have not received an urgent transplant due to a device malfunction.

A Subject will be considered a failure if they:

- Expire prior to 24 months, or
- Experience a stroke with a modified Rankin Score > 3 prior to 24 months, or
- Have a device replaced or exchanged or deactivated for any reason other than myocardial recovery prior to 24 months, or
- Have received an urgent transplant due to a LVAS malfunction prior to 24 months, or

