- Have withdrawn from the study for any reason prior to 24 months

The 24 month success rate of the HM III Subjects will be compared to the HM II control. The null and alternative hypotheses are:

$$H_0: \pi_{HM III} \leq \pi_{HM II} - \Delta$$
$$H_A: \pi_{HM III} > \pi_{HM II} - \Delta$$

where $\pi_{HM III}$ and $\pi_{HM II}$ are the long term success rates of HM III and HM II, respectively, and where Δ is the non-inferiority margin.

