8.8 Analysis of Survival and Subject Outcome

Overall survival will be assessed for each of the two treatments using the Kaplan-Meier product-limit method. Differences between treatments in survival distributions will be analyzed using a logrank test. Subjects surviving will be censored at last known follow-up time point.

A competing outcome graph will be prepared at 6 months for short term results and 24 months for long term results.

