8.15.2 KCCQ

The KCCQ score will be assessed at baseline and then at 3, 6, 12, 18, and 24 months. Data will be analyzed using mixed modeling by comparing the KCCQ score at each assessment interval to the baseline score. The Short Term indication will be limited to the 3 and 6 month assessments. The Long Term indication will include all assessments until 24 months or outcome, whichever occurs first.

8.16 Powered secondary analysis:

In addition to the primary outcome, the study will be powered to test if HM III pump reliability is superior to HM II by analyzing the incidence of pump replacements. Randomization described in Section 13.4 will continue beyond the Subjects needed to power the primary endpoint until a sufficient sample size has been enrolled to test the secondary endpoint. The null and alternative hypotheses are:

$$H_0: \pi_{HM\ III} \geq \pi_{HM\ II}$$

$$H_A: \pi_{HM\ III} < \pi_{HM\ II}$$

where $\pi_{HM\ III}$ is the HM III pump replacement rate and $\pi_{HM\ II}$ is the HM II pump replacement rate.

Based on data contained in Thoratec's device tracking database, 7% of the HM II Subjects receive a pump replacement by 24 months. If we assume that HM III pump replacements will be reduced to 3% at 24 months, then 1028 Subjects (514 per arm) will be needed to prove superiority with a power of 80% and alpha = 0.05 (2-sided).

Once the 366 Subjects needed for the long term indication are enrolled, Thoratec will continue to randomize 662 more Subjects (331 HM III and 331 HM II) for this secondary analysis. Data for this secondary analysis is not needed for the short or long term indications, but rather will be used to provide additional labeling information.

The Subjects will be followed for 24 months or to outcome, whichever occurs first, and analyzed using the Fisher's exact test. Treatments will also be compared on time-to-pump replacement using the log-rank test where Subjects without a replacement are censored at last known follow-up. Otherwise, there will be no imputation of missing data for this analysis.

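### Subjects exchanged to a non-study pump are withdrawn without vital-status follow-up, so overall survival censors them at exchange; the bias is probably small and would tend to favour HM II

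*Protocol*

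**What the plan says.** Protocol section 5 (Study Design) states: "Subjects who receive a device exchange to any device other than HM II or HM3, at any time during the study, will be withdrawn". The same sentence ends their follow-up: such subjects "will be withdrawn from the study and will not be followed". Protocol section 22 (Subject Withdrawal) lists the event among the reasons for withdrawal: "Subject has pump exchanged to any device other than HM II or HM3". Neither section asks for vital status afterwards.

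Protocol 13.9 and SAP 8.8 analyse overall survival by Kaplan-Meier with the same censoring rule: "Subjects surviving will be censored at last known follow-up time point". The arms are then compared: "Differences between treatments in survival distributions will be analyzed using a logrank test". Neither document counts a third-device exchange as an event in this analysis or plans a sensitivity analysis for it. Multiple imputation is reserved for missing primary endpoints (Protocol 13.1, SAP section 7).

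The primary composite handles the same subjects differently. SAP 8.2 lists as failures both "Have a device replaced or exchanged or deactivated for reasons other than myocardial recovery prior to 6 months" and, for the long-term endpoint, "Have withdrawn from the study for any reason prior to 24 months", with matching rules at the other time point.

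**The concern.** Kaplan-Meier and the logrank test are valid if a censored subject has the same later risk of death as those still being followed. Here censoring is triggered by a clinical event, replacement of the pump, and not by an administrative cut-off. Protocol 13.5 links replacements to thrombus and to driveline damage, so the later risk of these subjects may well differ from that of subjects still followed.

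The plan also expects replacement to differ by arm. SAP 8.16 takes it that "7% of the HM II Subjects receive a pump replacement by 24 months" and assumes 3% for HM3. If third-device exchanges follow that pattern, one arm loses more follow-up than the other.

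At stake is a named analysis that bears on the purpose stated in the introductions to both documents, where survival is one of the benefits to be compared. Survival also recurs in the subgroup analyses. Deaths that were never collected cannot be recovered at the analysis stage.

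**Working it through.** **1. The plan's replacement rates.** SAP 8.16 gives 7% against 3% at 24 months, two-sided alpha 0.05 and 80% power, hence 1028 subjects (514 per arm). The pooled-variance formula gives

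n = [1.96·√(2·0.05·0.95) + 0.8416·√(0.07·0.93 + 0.03·0.97)]² / 0.04² = 465 per arm.

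With continuity correction, (n/4)·[1 + √(1 + 4/(n·0.04))]² = 514 per arm. The figure of 1028 is reproduced, so the two rates are used below. The survival comparison has no stated size or power to reproduce.

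**2. How many subjects the rule could reach.** These rates cover all replacements. Exchanges to HM II or HM3 stay in follow-up, and the share going to a third device is not given. At 183 per arm, replacements number 0.07 × 183 = 12.8 (HM II) and 0.03 × 183 = 5.5 (HM3).

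| Assumed third-device share | HM II | HM3 |
|---|---|---|
| 25% | 3.2 | 1.4 |
| 50% | 6.4 | 2.7 |
| 100% | 12.8 | 5.5 |

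**3. Unobserved deaths are not the bias.** With a 25% share and 30-50% mortality after exchange (both assumptions), unobserved deaths are 3.2 × 0.3 to 0.5 = 1.0-1.6 for HM II and 1.4 × 0.3 to 0.5 = 0.4-0.7 for HM3. Kaplan-Meier, however, gives a censored subject the average risk of those still followed. Only the excess over that risk biases the curve.

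**4. Net bias with exchange at month 12 (assumption) and a constant hazard.** The remaining mortality of those still followed is 1 − √S, where S is 24-month survival. Protocol Table 1 puts death at 24 months at no more than 47% (S = 0.53); 20% is an assumed lower value. The bias is the proportion of the arm affected times the excess mortality. The proportions are 0.07 × 0.25 = 1.75% (HM II) and 0.03 × 0.25 = 0.75% (HM3). Each pair below is for 30% and 50% mortality after exchange.

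| Cohort mortality | 1 − √S | Excess (points) | HM II bias (points) | HM3 bias (points) | Gap (points) |
|---|---|---|---|---|---|
| 47% | 27.2% | 2.8 / 22.8 | 0.05 / 0.40 | 0.02 / 0.17 | 0.03 / 0.23 |
| 20% | 10.6% | 19.4 / 39.4 | 0.34 / 0.69 | 0.15 / 0.30 | 0.19 / 0.39 |

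**5. Cross-check with exchange spread over 24 months.** Let λ be the death hazard, h the third-device exchange hazard and m the multiple of λ after exchange. True survival is

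exp[−24(λ + h)] + ∫₀²⁴ h·exp[−(λ + h)t]·exp[−mλ(24 − t)] dt,

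while Kaplan-Meier estimates exp(−24λ). With S from 0.53 to 0.80, survival is overstated, in points, by:

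| Share | m | HM II | HM3 |
|---|---|---|---|
| any | 1 | 0 | 0 |
| 25% | 2 | 0.15-0.24 | 0.06-0.10 |
| 25% | 5 | 0.5-0.6 | 0.2-0.3 |
| 100% | 2 | 0.6-1.0 | 0.2-0.4 |
| 100% | 5 | 1.9-2.4 | 0.8-1.0 |
| 100% | immediate death | 3.7-5.6 | 1.6-2.4 |

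The last row is a bound and not a plausible case.

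**The case against.** The strongest reply is that nothing decisive depends on this analysis. Overall survival is not in the lists of secondary endpoints (Protocol 10.2, SAP 5.3) and has no hypothesis, margin, alpha allocation or power. SAP section 7 also disclaims statistical claims on secondary endpoints. This stands, and it is why the point is minor.

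It can also be said that follow-up already ends at transplant, explant or death (Protocol section 8), so stopping when no study pump remains is consistent. This stands only in part. A subject exchanged to HM II or HM3 is not withdrawn, so exchange in itself does not end follow-up. Whether survival is known then depends on the make of the new pump.

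Third, the documents give no share of replacements going to another make, and it could be close to zero. This stands, and any size is therefore conditional.

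Three stronger readings are tempting, and the documents do not support them:

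- A reader might infer that the primary result is biased. It is not by this route: exchange and withdrawal both count as failures. In the powered secondary analysis the replacement is itself the event.
- A reader might take 7% and 3% as the rates of censoring. They are rates of all replacements, and the plan assumes nothing about third-device exchange.
- A reader might suppose that the rule helps the investigational device, or that every such exchange is a pump failure. The rule covers exchange for any reason. With more exchanges on HM II and a worse outlook afterwards, the censoring flatters HM II.

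**Conclusion.** The concern holds as a minor one. Followed as written, the plan censors third-device exchanges in the overall-survival comparison at a point that is likely informative, and no later data or sensitivity analysis would reveal the effect.

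Under the month-12 assumptions in step 4, HM II survival is overstated by about 0.05-0.7 points and the between-arm difference is off by about 0.03-0.4 points. Even if every replacement went to a third device, the overstatement stays at about 2.4 points or less per arm unless the hazard of death afterwards exceeds five times that of other subjects. It is zero if the hazard does not change.

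The third-device share, the timing of exchange and the mortality afterwards are assumptions; only the replacement rates, the arm size and the 47% ceiling on death come from the documents. The direction depends on which arm has more such exchanges. On the plan's expectation it works against HM3, so it could mask an HM3 survival advantage but would not create one.

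**What to change.** Amend Protocol sections 5 and 22 so that a subject exchanged to another device stops study visits but, where consent allows, has vital status and date of death collected to 24 months. The date is needed because status at fixed times alone gives Kaplan-Meier and the logrank test no event time.

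State in Protocol 13.9 and SAP 8.8 that overall survival is analysed in all randomized subjects using these data. Neither section names a population at present, and the documents assign intent-to-treat to the primary endpoint but As Treated to the secondary endpoints. Keep censoring at exchange as a sensitivity analysis.

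The cost is consent wording plus a chart or phone check for a handful of subjects: about 3 HM II and 1 HM3 in the 366-subject cohort at a 25% share, and at most about 13 and 6. The planned sizes of 294, 366 and 1028, the alpha levels and clinical management do not change. Adverse-event and quality-of-life data after exchange would still be missing.

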6 STUDY POPULATION

Advanced heart failure NYHA Class III patients with dyspnea upon mild physical activity, or NYHA Class IV patients who are refractory to advanced heart failure management.

7 NUMBER OF CLINICAL SITES AND SUBJECTS

The study will be conducted in up to 70 clinical sites. The total sample size for this study is 1028 Subjects. Three hundred and sixty-six (366) Subjects will be enrolled and randomized to evaluate the primary endpoint. The data from the Subjects randomized for the primary endpoint will be used for PMA submission for the Short Term and Long Term indications. An additional 662 Subjects will be randomized to achieve 1028 Subjects needed for the powered secondary endpoint analysis. The data from the powered secondary endpoint will be used to update labeling under a Supplemental PMA. Refer to Figure 2.

8 STUDY DURATION

It is anticipated that it will take approximately 6 months to complete the early safety assessment phase of the study. After that, the first 5 U.S. centers will continue to enroll up to a total of 30 subjects (including those in the early safety analysis) while the IDE Supplement is under review with the FDA for full IDE approval to expand the study to 60 centers.

It is anticipated that it will take approximately 42 months to complete enrollment and follow up for the primary endpoint analysis of the study for the short and long term evaluation of the device. All randomized Subjects needed for the primary endpoint analysis will be followed for 24 months or to outcome (transplant, explant, or death), whichever occurs first.

It is anticipated that it will take approximately 13 additional months to enroll the randomized Subjects for the powered secondary endpoint. All randomized Subjects that are not required for the primary endpoint analysis will be followed for 24 months or to outcome, whichever occurs first.

9 STUDY OBJECTIVES

9.1 Primary Study Objective

The primary objective of the study is to evaluate the safety and effectiveness of the HM3 LVAS by demonstrating non-inferiority to the HM II LVAS when used for the treatment of advanced, refractory, left ventricular heart failure.

9.2 Secondary Study Objectives

Secondary objectives include:

- Assessment of adverse events
- Assessment of rehospitalizations and re-operations
- Assessment of quality of life and functional status
- Assessment of clinical reliability, device malfunctions, and device failures

10 CLINICAL STUDY ENDPOINTS

10.1 Primary Study Endpoints

- Composite of survival to transplant, recovery or 6 months of LVAD support free of debilitating stroke (Modified Rankin Score > 3) or reoperation to replace the pump
- Composite of survival to transplant, recovery or 24 months of LVAD support free of debilitating stroke (Modified Rankin Score > 3) or reoperation to replace the pump

The 6 month composite data will be submitted for the short term indication and the 24 month composite data will be submitted for the long term indication.

10.2 Secondary Study Endpoints

- Quality of Life: Quality of Life as measured by the EuroQoL-5D-5L (EQ-5D-5L) and the Kansas City Cardiomyopathy Questionnaire (KCCQ)
- Functional Status: Functional status as measured by the Six Minute Walk Test (6MWT) and by NYHA Classification.
- Adverse Events: Frequency, incidence and rates of pre-defined anticipated adverse events
- Device Malfunctions: Frequency and incidence of device malfunctions
- Reoperations: Frequency and incidence of all reoperations
- Rehospitalizations: Frequency and incidence of all rehospitalizations

10.3 Powered Secondary Endpoint

- Incidence of pump replacements at 24 months

11 INCLUSION CRITERIA

- 1) Subject or legal representative has signed Informed Consent Form (ICF)
- 2) Age \geq 18 years
- 3) BSA \geq 1.2 m²
- 4) NYHA Class III with dyspnea upon mild physical activity or NYHA Class IV
- 5) LVEF \leq 25%
- 6) a) Inotrope dependent

OR

b) CI < 2.2 L/min/m², while not on inotropes and subjects must also meet one of the following:

- On optimal medical management (OMM), based on current heart failure practice guidelines for at least 45 out of the last 60 days and are failing to respond
 - Advanced heart failure for at least 14 days AND dependent on intra-aortic balloon pump (IABP) for at least 7 days,
- 7) Females of child bearing age must agree to use adequate contraception

12 EXCLUSION CRITERIA

- 1) Etiology of HF due to or associated with uncorrected thyroid disease, obstructive cardiomyopathy, pericardial disease, amyloidosis, or restrictive cardiomyopathy
- 2) Technical obstacles which pose an inordinately high surgical risk, in the judgment of the investigator
- 3) Existence of ongoing mechanical circulatory support (MCS) other than IABP
- 4) Positive pregnancy test if of childbearing potential
- 5) Presence of mechanical aortic cardiac valve that will not be either converted to a bioprosthesis or oversewn at the time of LVAD implant
- 6) History of any organ transplant
- 7) Platelet count $< 100,000 \times 10^3/L$ ($< 100,000/ml$)
- 8) Psychiatric disease/disorder, irreversible cognitive dysfunction or psychosocial issues that are likely to impair compliance with the study protocol and LVAS management
- 9) History of confirmed, untreated Abdominal Aortic Aneurysm (AAA) > 5 cm in diameter within 6 months of enrollment
- 10) Presence of an active, uncontrolled infection
- 11) Intolerance to anticoagulant or antiplatelet therapies or any other peri/post-operative therapy that the investigator will require based upon the patients' health status
- 12) Presence of any one of the following risk factors for indications of severe end organ dysfunction or failure:
 - a) An INR ≥ 2.0 not due to anticoagulation therapy
 - b) Total bilirubin > 43 $\mu\text{mol/L}$ (2.5 mg/dl), shock liver, or biopsy proven liver cirrhosis
 - c) History of severe chronic obstructive pulmonary disease (COPD) defined by $\text{FEV}_1/\text{FVC} < 0.7$, and $\text{FEV}_1 < 50\%$ predicted
 - d) Fixed pulmonary hypertension with a most recent PVR ≥ 8 Wood units that is unresponsive to pharmacologic intervention
 - e) History of stroke within 90 days prior to enrollment, or a history of cerebrovascular disease with significant ($> 80\%$) uncorrected carotid artery stenosis
 - f) Serum Creatinine ≥ 221 $\mu\text{mol/L}$ (2.5 mg/dl) or the need for chronic renal replacement therapy
 - g) Significant peripheral vascular disease (PVD) accompanied by rest pain or extremity ulceration
- 13) Patient has moderate to severe aortic insufficiency without plans for correction during pump implant
- 14) Pre albumin < 150 mg/L (15mg/dL) or Albumin < 30 g/L (3 g/dL) (if only one available); pre albumin < 150 mg/L (15mg/dL) and Albumin < 30 g/L (3 g/dL) (if both available)
- 15) Planned Bi-VAD support prior to enrollment
- 16) Patient has known hypo or hyper coagulable states such as disseminated intravascular coagulation and heparin induced thrombocytopenia

- 17) Participation in any other clinical investigation that is likely to confound study results or affect the study
- 18) Any condition other than HF that could limit survival to less than 24 months

